Each data will be analyzed separately and presented descriptively as a mean and standard deviation. Furthermore, each variable will be subjected to independent two-tailed t-tests to determine statistically-significant differences between the two experimental arms. Given the diversity of outcomes and the fact that they are largely independent, there does not appear to be the need to perform a Bonferroni adjustment to avoid Type I error. However, the data will be scrupulously analyzed and if evidence of Type I error is observed, such an adjustment will be made.

Timeline.

It is anticipated that the project will take approximately 12 months to complete. We estimate that recruitment and treatment will take place in 11 months and that there will be a 1-month period of data analysis.

Research Staff.

The following are the research staff for this study and their roles:

[name], Director, NYU Voice Center, Associate Professor, Dept. of Otolaryngology – will perform videostroboscopy and he has expertise in the diagnosis and management of vocal pathology.

[name], Assistant Professor, Dept. of Otolaryngology – will collect voice recordings and aerodynamic measures and has expertise in voice evaluation and conducting voice research.

[name], MA, CCC-SLP, Rusk Institute of Rehabilitation – will provide voice therapy. She is a voice pathologist and specialist in the rehabilitation of the injured voice.

[name] MD, NYU Voice Center – will be the study coordinator. He is a research associate and has expertise in conducting voice related research.

Facilities.

The research will be conducted at the clinical offices of [name] (PI), located at [name] and at Rusk Rehabilitation Outpatients Services, ACC- [name]. The offices have the necessary equipment, personnel, and computer hardware/software for conducting the study.

Limitations.

We acknowledge that there are certain limitations to this study. The study sample size is relatively small, although sample size calculations determine that we should be able to demonstrate a significant change if one exists, our results would certainly be more robust with a larger cohort. In this regard, we are limited by budget constraints, since the study is relatively expensive to run. The other major limitation of the study is that we are not differentiating between lesion types. We feel that this is quite difficult to do in reality, since vocal fold lesions, even within a type, are quite variable. Of course, we could theoretically conduct a post-hoc analysis of lesion type as a variable, but our cohort size is likely too small for this.

Future Directions.

In the future, we will need to address the limitations by opening up a multicenter, prospective trial of oral steroids for benign phonotraumatic vocal fold lesions. In this larger trial, it will be possible to differentiate effects of steroids on different lesion types. In addition, it may be possible to investigate dose and formulation effects of different steroids.

This project is a small part of a larger research program examining the role of glucocorticoids for clinical use for laryngeal lesions. In addition to studying the use of oral steroids, we will also study the effects of intralesional steroids for a variety of vocal fold lesions types, including vocal fold fibrosis, which remains a major clinical problem.

REFERENCES

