In addition, the study will also investigate the potential added advantage of the use of steroids in patients undergoing voice therapy. We hypothesize that oral steroids will lead to a reduction in lesion size, which will substantially aid in the delivery and incorporation of voice therapy techniques, since the reduced lesion size will likely improve glottal closure and reduce vocal fold mass, thereby improving the overall laryngeal biomechanics and providing an ideal starting point for behavioral voice therapy.

(c) Approach

Subjects and Protocol

The specific aim of this project is to determine the effectiveness of a short course of oral steroids prior to the initiation of behavioral voice therapy in patients with benign, phonotraumatic vocal fold lesions. As mentioned above, the study is designed to be prospective, randomized, and controlled. The study group will be recruited from our patient population. Our Center serves the population of the greater metropolitan New York area and has a high volume of patients that present with benign, phonotraumatic vocal fold lesions. Subjects that are non-surgical candidates that are assigned to receive voice therapy at our institution by a single voice therapist ([name]) will be eligible for the study. Potential subjects will be identified by the PI or research staff and will be enrolled right after their clinical visit if they agree to the study protocol and do not meet the exclusion criteria (**Figure 1**). Recruitment will be done solely from the PI's clinical practice. The PI ([name]), research coordinator ([name]) or the co-Investigators ([name], [name]) will be obtaining written consent after their clinical visit. Participants will be provided a copy of the completed consent form. Subjects are free not to participate in the study and their decision will not alter the quality of medical treatment that they will be receiving.

At the time of enrollment, the study coordinator will open a pre-sealed envelope that will assign a subject to either receive oral steroids or placebo prior to the initiation of voice therapy. There will be twenty envelopes each that will read either "steroid" or "placebo". Replacement envelopes will be added if/when subjects drop out from the study.

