According to their assignment, subjects will then be dispensed pills and counseled on proper dosing and potential side effects. Subjects assigned to the "steroid" arm will be prescribed two 20 mg prednisone doses per day (40 mg total), taken together in the morning for four days. This dose was chosen as it is the most common dose used in our practice and is within the lower part of the starting range recommended for this drug for the treatment of other inflammatory conditions of the airway, including asthma. A four-day treatment regimen has demonstrated efficacy in our experience, while reducing the risk of side effects.

The therapist ([name]), the scientist that will be conducting the evaluation ([name]) and other individuals involved in collection and analysis of data will be blinded as to whether the subject received drug. The prescribing physician (also the PI) will not be blinded, as this would interfere with routine clinical care of the subject. The research assistant ([name]) will also be non-blinded, as he will be in charge of the randomization and tracking process. Neither of these two individuals will be directly involved in providing or directing therapy, nor will be involved in collection or analysis of the data.

Prior to the initiation of therapy, subjects will be asked to return for an "interval evaluation", which is a research visit. During this evaluation, subjects will undergo videostroboscopy and voice evaluation by one of the co-investigators ([name]). Measures to be collected are described in the following section. Subjects will be reimbursed \$75 for the time and expense involved in returning for this research evaluation, which is considered outside of routine clinical care. The charges for this visit will also be paid by the research account for the same reason.

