Subjects will then enter the voice therapy part of the protocol. They will receive an initial evaluation, which is part of routine clinical care. This evaluation will be used to determine the best mode of therapy to pursue. Subjects will receive the form of therapy that specifically meets their needs. The therapist will then keep records of the subject's progress, including a timeline of progress. Subjects will be asked to maintain a regular schedule with the therapist, as this is ideal and will allow for better tracking of time to improvement. During therapy, subjects will be asked to fill out VHI-10 forms on a bi-weekly basis. These forms will be collected for study purposes.

At the completion of therapy, subjects will follow-up with the treating physician ([name]) for a routine follow-up clinical visit. During this visit, routine videostroboscopy and voice evaluation by the co-investigator ([name]) will take place. The general experimental design is summarized in **Figure 2**.

Dependent Variables and Data Collection (Figure 3)

- 1. Voice Handicap Index (VHI)-10.** The primary dependent variable is difference in VHI-10 scores from baseline (pre-treatment). The VHI-10 is a standardized and validated instrument that measures patient perception of their voice disorder.(29) It is administered routinely as a component of clinical care at the NYU Voice Center. Completed forms are scanned into the patient's electronic medical record for easy access and longitudinal comparison. For this study, VHI-10 data will be collected during the initial, interval, and final evaluations.

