Subjects enrolled in the study will be asked to take either steroid or placebo as described above. Although oral steroids are used regularly in the management of benign vocal fold lesions, in this study we randomize the subjects that will receive steroids versus placebo. This is therefore considered a specific research procedure.

Subjects enrolled in the study will also undergo the data collection procedures described in the section above entitled “Dependent Variables and Data Collection” a total of three times. The initial set of procedures will be performed on the initial visit as a part of the routine clinical care for which the subject is visiting the NYU Voice Center. Similarly, the final study visit is considered part of routine clinical care and the procedures performed will not be performed specifically for research purposes. The procedures performed on the second or interval visit will be considered “research procedures”, since they are being performed outside of routine clinical care. Subjects will be reimbursed for their time and expense in participating in the interval visit and their visit costs will be covered by the study account for this visit as described above. A specific explanation of the procedures that will occur during each visit is provided below (each visit has the same set of procedures):

The patient will complete the Voice Handicap Index (VHI)-10 upon arrival to the clinic. An Audio-perceptual Analysis and an Aerodynamic Analysis of Voice will be performed in the voice lab the speech pathologist ([name] or [name]). Finally, the patient will be brought to the examination room, where a history and physical examination will be performed, followed by videostroboscopy.

Investigational Drug Use.

As mentioned, subjects will be randomized to receive prednisone or placebo. Prednisone is a drug product lawfully marketed in the U.S. The investigation is not intended to be reported to the FDA as a well-controlled study in support of a new indication for use and is not intended to be used to support any other significant change in the labeling for the drug. The investigation is not intended to support a significant change in the advertising for the product. The route, dose and indication of the medication will be as per FDA approval. The investigation is conducted in compliance with the requirements for IRB review set forth in 21 CFR Part 56 and with the requirements for informed consent set forth in 21 CFR

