Presence of phonotraumatic lesion deemed to be etiologic for the complaint of dysphonia	Known allergy or hypersensitivity to oral steroids
Voice therapy deemed to be the primary (or at least initial) treatment to address the dysphonia	Active infection
Willingness to be an active participant in voice therapy	Diabetes Mellitus
	Prior history of radiation to the neck
	Recent myocardial infarction
	Recent gastrointestinal surgery with bowel anastomosis (3 months)
	Active peptic ulcer
	Pregnancy
	Severe depression or history of psychosis
	History of recent laryngeal surgery (within 12 months)
Figure 1. Inclusion and exclusion criteria for the proposed trial.	

Figure 2

[figure not shown]

Figure 3

Dependent Variable	Brief Description
VHI (primary dependent variable)	The change in VHI-10 scores from pre-treatment to following treatment
Video-Perceptual Analysis	Analysis of stroboscopic parameters by expert raters as well as quantification of lesion size
Audio-Perceptual Analysis	The CAPE-V stimuli will be analyzed using a visual analog scale with expert listeners
Aerodynamic Voice Analysis	Collection of acoustic output (dB) and pulmonary pressure (cmH2O) during /pa/

Figure 3. Dependent variables to be analyzed in the current proposal.

Figure 4

[figure not shown]

Figure 4: This image shows the methodology of quantifying lesion size. (A) Representative image of right vocal fold polyp. (B) Lesion area and vocal fold length to be measured. (C) Angle of anterior commissure to be measured.

Name _____

Date _____

I would rate my degree of talkativeness as the following: (circle response)

1	2	3	4	5	6	7
Quiet Listener			Average Talker			Extremely Talkative

FOR STAFF USE	
1- TALK	_____
2- VHI-10	_____
3- RSI	_____
4- SVHI-10	_____

VHI-10 Instructions: These are statements that many people have used to describe their voices and the effects of their voices on their lives. Circle the response that indicates how frequently you have the same experience.

My voice makes it difficult for people to hear me.	0	1	2	3	4
People have difficulty understanding me in a noisy room.	0	1	2	3	4
My voice difficulties restrict personal and social life.	0	1	2	3	4
I feel left out of conversations because of my voice.	0	1	2	3	4
My voice problem causes me to lose income.	0	1	2	3	4
I feel as though I have to strain to produce voice.	0	1	2	3	4
The clarity of my voice is unpredictable.	0	1	2	3	4
My voice problem upsets me.	0	1	2	3	4

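### The primary t-test uses the initial VHI-10 only by subtraction; entering it as a covariate usually gains precision and costs about 1 power point at worst

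*Combined protocol and SAP*

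**What the plan says.** Figure 3 describes the primary dependent variable as "The change in VHI-10 scores from pre-treatment to following treatment", and item 1 of Dependent Variables and Data Collection likewise defines it as a difference from the pre-treatment score. The analysis paragraph of Sample Size and Statistical Considerations then says that "each variable will be subjected to independent two-tailed t-tests to determine statistically-significant differences between the two experimental arms". The Data Analysis paragraph adds only comparisons between visits. No covariate, regression model or stratified allocation appears in the documents.

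The initial score is available for every subject: "For this study, VHI-10 data will be collected during the initial, interval, and final evaluations". It also comes before randomization. Research Versus Non-Research Procedures states: "The patient will complete the Voice Handicap Index (VHI)-10 upon arrival to the clinic". Subjects and Protocol says that patients "will be enrolled right after their clinical visit", and then: "At the time of enrollment, the study coordinator will open a pre-sealed envelope".

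**The concern.** A change score uses the initial value in one fixed way: it assumes that each extra point at the start carries through as exactly one extra point at the end. If the true slope differs from 1, change remains correlated with the initial score, and that avoidable variation stays in the error term. ANCOVA estimates the slope instead.

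There is a structural reason to expect such a correlation here. The VHI-10 has ten items scored 0 to 4, so totals run from 0 to 40, and Figure 1 sets no minimum score for entry. A subject who starts at 8 cannot improve by the 10 or 14 points assumed in the sample size, whereas one who starts at 30 can. This does not fix the size of the correlation, but it argues against taking it to be zero.

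Limitations says that budget restricts the cohort, so precision from data already in hand is worth taking. Chance imbalance also matters at this size. The difference in mean initial score between arms has a standard error of √(2/20) = 0.316 SD, so an imbalance of 0.5 SD or more (z = 0.5/0.316 = 1.58) occurs in about 11% of trials. If the slope is not 1, that imbalance shifts the unadjusted estimate.

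**Working it through.** **Inputs from Sample Size and Statistical Considerations.** Mean change 10 and 14, so the difference is 4; SD of change 7 in both arms; alpha 0.05; 20 per arm. The test is two-tailed. I take all 20 per arm as analysed, since Subjects and Protocol provides for replacement of dropouts.

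**Inputs not in the documents (assumed and varied).** r, the correlation of initial with final VHI-10, and k, the final SD divided by the initial SD.

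**The plan's own figure.** By the normal formula, n per arm = 2 × (1.960 + 0.842)² × 49/16 = 48.1, so 49; the exact t calculation gives 50. The stated 20 per arm is not reproduced.

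**Planned t-test at 20 per arm.** SE = 7 × √(2/20) = 2.214 on 38 df. Noncentral-t power is 42.1%, and the half-width is 2.024 × 2.214 = 4.48.

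**ANCOVA.** Let s be the initial SD.
- Var(change) = s²(1 + k² − 2rk), set to 49.
- Residual variance = k²s²(1 − r²).
- Ratio of residual variance to 49: R = k²(1 − r²)/(1 + k² − 2rk).
- Variance of the adjusted difference = 49R × (2/20) × (1 + 1/36) on 37 df. The factor 37/36 is the average cost of estimating the slope.
- Equivalent unadjusted n per arm = 20/(R × 37/36).

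Example, k = 1 and r = 0.5: R = 0.75, variance = 36.75 × 0.1 × 1.0278 = 3.777, SE = 1.943, half-width = 2.026 × 1.943 = 3.94, equivalent n = 25.9.

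| k | r | R | Power | Half-width | Equivalent n per arm |
|---|---|---|---|---|---|
| t-test | – | – | 42.1% | 4.48 | 20 |
| 1 | 0.3 | 0.650 | 57.7% | 3.67 | 29.9 |
| 1 | 0.5 | 0.750 | 51.8% | 3.94 | 25.9 |
| 1 | 0.7 | 0.850 | 46.9% | 4.19 | 22.9 |
| 1 | 0.9 | 0.950 | 42.9% | 4.43 | 20.5 |
| 0.7 | 0.3 | 0.417 | 76.7% | 2.94 | 46.7 |
| 0.7 | 0.5 | 0.465 | 72.1% | 3.10 | 41.8 |
| 0.7 | 0.7 | 0.490 | 69.8% | 3.18 | 39.7 |
| 1.3 | 0.3 | 0.805 | 49.0% | 4.08 | 24.2 |
| 1.3 | 0.5 | 0.912 | 44.4% | 4.34 | 21.3 |
| 1.3 | 0.7 | 0.991 | 41.5% | 4.53 | 19.6 |
| slope exactly 1 | – | 1 | 41.2% | 4.55 | 19.5 |

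**Break-even.** ANCOVA has the smaller SE when R × 37/36 < 1, that is, when the absolute correlation of initial score with change exceeds √(1/37) = 0.164 (0.168 on power, 0.170 on half-width). That correlation is (kr − 1)/√(1 + k² − 2rk). The t-test therefore has the higher power only for r above about 0.94 when k = 1, for r of 0.64 to 0.86 (slopes of about 0.83 to 1.11) when k = 1.3, and at no r when k = 0.7.

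**Largest loss.** At the plan's difference of 4 it is 42.1 − 41.2 = 0.9 point. Over all differences at this n it is 1.2 points, at a difference of about 5.5.

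**Simulation.** With 100,000 normal-data trials per setting and the slope estimated, ANCOVA power was 57.6, 51.8, 47.0 and 43.1% at r = 0.3, 0.5, 0.7 and 0.9 (k = 1), and 41.3% at slope 1. Type I error was 4.8 to 5.1% for both tests.

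**Does it rescue the sample size?** No. For 80% power ANCOVA needs 33, 38, 43 or 48 per arm at r = 0.3, 0.5, 0.7 or 0.9 with equal SDs, against 50 for the t-test.

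**The case against.** The t-test is valid, pre-specified and consistent with the assumptions behind the sample size, so nothing here is an error. That is accepted: this is an improvement.

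The gain rests on r and k, which the documents do not give. The figures near 70 to 77% need a final SD well below the initial one, and with k = 1.3 the gain is small or slightly negative. This also stands. It limits what can be said about size, but not the decision, because the loss is bounded at about 1 point while the gain can be many times that.

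Naming the covariate in advance prevents a later choice between adjusted and unadjusted results, but the plan already names a single test, so a later adjusted result would be a visible departure. That benefit is therefore minor. It matters mainly because an adjusted analysis is worth having only if it is fixed before the data are seen.

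Three points bear on the wording of the fix. The plan is loose about which visit defines the primary change, since the Data Analysis paragraph makes the initial-to-final comparison conditional. Lesion size may be measured on both sides and CAPE-V is scored by three listeners, so a single initial value per subject must be defined first. A statement that the sample size assumes no gain from adjustment could make 20 per arm look conservative, which it is not. All three are dealt with in the fix; none removes the case for adjustment.

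**Conclusion.** The point holds as an efficiency improvement that should be made. It is certain that no covariate is planned and that the initial VHI-10 precedes randomization. With equal SDs, adjustment adds about 15.6, 9.7, 4.8 and 0.8 power points at r = 0.3, 0.5, 0.7 and 0.9, and at r = 0.5 it makes 20 per arm worth about 26. At worst it makes 20 per arm worth about 19.5. Confidence is high in the absence of the covariate and in the small downside, but not in the size of the gain. The calculations assume normal data, a common slope in both arms and 20 analysed per arm. The shortfall against 80% power is a separate and larger problem that this change does not solve.

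**What to change.** In the analysis paragraph of Sample Size and Statistical Considerations:

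1. Make the primary analysis an ANCOVA of VHI-10 change (or, equivalently for the arm effect, of VHI-10 at that visit) on arm plus initial VHI-10. Name the visit, and report the adjusted difference with its 95% CI.
2. State that the interval score is never a covariate for the arm comparison, because it follows study drug: "Prior to the initiation of therapy, subjects will be asked to return for an" interval evaluation, after the pills have been dispensed.
3. Keep the unadjusted t-test on change as a sensitivity analysis.
4. Use the same model, with each outcome's own initial value, for lesion size ratio, CAPE-V and the aerodynamic measures, once each is reduced to one value per subject and visit. The paired stroboscopy ratings are already relative and have no initial value, so they stay outside this change.

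In the sample-size paragraph, say that the calculation was based on unadjusted change and takes no credit for adjustment. Add this together with a corrected sample size, not on its own.

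The cost is about four sentences, one degree of freedom, no new data, and about 1 power point if initial score and change prove nearly uncorrelated.

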Presence of phonotraumatic lesion deemed to be etiologic for the complaint of dysphonia	Known allergy or hypersensitivity to oral steroids
Voice therapy deemed to be the primary (or at least initial) treatment to address the dysphonia	Active infection
Willingness to be an active participant in voice therapy	Diabetes Mellitus
	Prior history of radiation to the neck
	Recent myocardial infarction
	Recent gastrointestinal surgery with bowel anastomosis (3 months)
	Active peptic ulcer
	Pregnancy
	Severe depression or history of psychosis
	History of recent laryngeal surgery (within 12 months)
Figure 1. Inclusion and exclusion criteria for the proposed trial.	

Figure 2

[figure not shown]

Figure 3

Dependent Variable	Brief Description
VHI (primary dependent variable)	The change in VHI-10 scores from pre-treatment to following treatment
Video-Perceptual Analysis	Analysis of stroboscopic parameters by expert raters as well as quantification of lesion size
Audio-Perceptual Analysis	The CAPE-V stimuli will be analyzed using a visual analog scale with expert listeners
Aerodynamic Voice Analysis	Collection of acoustic output (dB) and pulmonary pressure (cmH2O) during /pa/

Figure 3. Dependent variables to be analyzed in the current proposal.

Figure 4

[figure not shown]

Figure 4: This image shows the methodology of quantifying lesion size. (A) Representative image of right vocal fold polyp. (B) Lesion area and vocal fold length to be measured. (C) Angle of anterior commissure to be measured.

Name _____

Date _____

I would rate my degree of talkativeness as the following: (circle response)

1	2	3	4	5	6	7
Quiet Listener			Average Talker			Extremely Talkative

FOR STAFF USE	
1- TALK	_____
2- VHI-10	_____
3- RSI	_____
4- SVHI-10	_____

VHI-10 Instructions: These are statements that many people have used to describe their voices and the effects of their voices on their lives. Circle the response that indicates how frequently you have the same experience.

My voice makes it difficult for people to hear me.	0	1	2	3	4
People have difficulty understanding me in a noisy room.	0	1	2	3	4
My voice difficulties restrict personal and social life.	0	1	2	3	4
I feel left out of conversations because of my voice.	0	1	2	3	4
My voice problem causes me to lose income.	0	1	2	3	4
I feel as though I have to strain to produce voice.	0	1	2	3	4
The clarity of my voice is unpredictable.	0	1	2	3	4
My voice problem upsets me.	0	1	2	3	4
My voice makes me feel handicapped.	0	1	2	3	4
People ask "What's wrong with your voice?"	0	1	2	3	4

0 = Never
1 = Almost never
2 = Sometimes
3 = Almost always
4 = Always

Please check that you have answered all the questions.

RSI Instructions: These are statements that many people have used to describe their voices and the effects of their voices on their lives. Circle the response that indicates how frequently you have the same experience.

Within the last **MONTH**, how did the following problems affect you?

0 = No problem 5 = Severe problem
--------------------------	--------------------------

Hoarseness or a problem with your voice	0	1	2	3	4	5
Clearing your throat	0	1	2	3	4	5
Excess throat mucous	0	1	2	3	4	5
Difficulty swallowing food, liquids or pills	0	1	2	3	4	5
Coughing after eating or after lying down	0	1	2	3	4	5
Breathing difficulties or choking episodes	0	1	2	3	4	5
Troublesome or annoying cough	0	1	2	3	4	5
Sensations of something sticking in your throat or a lump in your throat	0	1	2	3	4	5
Heartburn, chest pain, indigestion, or stomach acid coming up	0	1	2	3	4	5

Please check that you have answered all the questions.

IF YOU ARE A SINGER, PLEASE COMPLETE THE BACK OF THE PAGE.

DELTASONE - prednisone tablet

Pharmacia and Upjohn and Company

DESCRIPTION

DELTASONE Tablets contain prednisone which is a glucocorticoid. Glucocorticoids are adrenocortical steroids, both naturally occurring and synthetic, which are readily absorbed from the gastrointestinal tract. Prednisone is a white to practically white, odorless, crystalline powder. It is very slightly soluble in water; slightly soluble in alcohol, in chloroform, in dioxane, and in methanol.

The chemical name for prednisone is pregna-1,4-diene-3,11,20-trione, 17,21-dihydroxy- and its molecular weight is 358.43.

The structural formula is represented below:

DELTASONE Tablets are available in 5 strengths: 2.5 mg, 5 mg, 10 mg, 20 mg and 50 mg. Inactive ingredients: **2.5 mg**—Calcium Stearate, Corn Starch, Erythrosine Sodium, Lactose, Mineral Oil, Sorbic Acid and Sucrose. **5 mg**—Calcium Stearate, Corn Starch, Lactose, Mineral Oil, Sorbic Acid and Sucrose. **10 mg**—Calcium Stearate, Corn Starch, Lactose, Sorbic Acid and Sucrose. **20 mg**—Calcium Stearate, Corn Starch, FD&C Yellow No. 6, Lactose, Sorbic Acid and Sucrose. **50 mg**—Corn Starch, Lactose, Magnesium Stearate, Sorbic Acid, Sucrose, and Talc.

ACTIONS

Naturally occurring glucocorticoids (hydrocortisone and cortisone), which also have salt-retaining properties, are used as replacement therapy in adrenocortical deficiency states. Their synthetic analogs are primarily used for their potent anti-inflammatory effects in disorders of many organ systems.

Glucocorticoids cause profound and varied metabolic effects. In addition, they modify the body's immune responses to diverse stimuli.

INDICATIONS

DELTASONE Tablets are indicated in the following conditions:

1. Endocrine Disorders

Primary or secondary adrenocortical insufficiency (hydrocortisone or cortisone is the first choice; synthetic analogs may be used in conjunction with mineralocorticoids where applicable; in infancy mineralocorticoid supplementation is of particular importance)

Congenital adrenal hyperplasia

Hypercalcemia associated with cancer

Nonsuppurative thyroiditis

2. Rheumatic Disorders

As adjunctive therapy for short-term administration (to tide the patient over an acute episode or exacerbation) in:

Psoriatic arthritis

Rheumatoid arthritis, including juvenile rheumatoid arthritis (selected cases may require low-dose maintenance therapy)

Ankylosing spondylitis

Acute and subacute bursitis

Acute nonspecific tenosynovitis

Acute gouty arthritis

Post-traumatic osteoarthritis

Synovitis of osteoarthritis

Epicondylitis

3. Collagen Diseases

During an exacerbation or as maintenance therapy in selected cases of:

Systemic lupus erythematosus

Systemic dermatomyositis (polymyositis)

Acute rheumatic carditis

4. Dermatologic Diseases

Pemphigus

Bullous dermatitis herpetiformis

Severe erythema multiforme (Stevens-Johnson syndrome)

Exfoliative dermatitis

Mycosis fungoides

Severe psoriasis

Severe seborrheic dermatitis

5. Allergic States

Control of severe or incapacitating allergic conditions intractable to adequate trials of conventional treatment:

Seasonal or perennial allergic rhinitis
Bronchial asthma
Contact dermatitis
Atopic dermatitis
Serum sickness
Drug hypersensitivity reactions

6. Ophthalmic Diseases

Severe acute and chronic allergic and inflammatory processes involving the eye and its adnexa such as:

Allergic corneal marginal ulcers
Herpes zoster ophthalmicus
Anterior segment inflammation
Diffuse posterior uveitis and choroiditis
Sympathetic ophthalmia
Allergic conjunctivitis
Keratitis
Chorioretinitis
Optic neuritis
Iritis and iridocyclitis

7. Respiratory Diseases

Symptomatic sarcoidosis
Loeffler's syndrome not manageable by other means
Berylliosis
Fulminating or disseminated pulmonary tuberculosis when used concurrently with appropriate antituberculous chemotherapy
Aspiration pneumonitis

8. Hematologic Disorders

Idiopathic thrombocytopenic purpura in adults
Secondary thrombocytopenia in adults
Acquired (autoimmune) hemolytic anemia
Erythroblastopenia (RBC anemia)
Congenital (erythroid) hypoplastic anemia

9. Neoplastic Diseases

For palliative management of:
Leukemias and lymphomas in adults
Acute leukemia of childhood

10. Edematous States

To induce a diuresis or remission of proteinuria in the nephrotic syndrome, without uremia, of the idiopathic type or that due to lupus erythematosus

11. Gastrointestinal Diseases

To tide the patient over a critical period of the disease in:
Ulcerative colitis
Regional enteritis

12. Nervous System

Acute exacerbations of multiple sclerosis

13. Miscellaneous

Tuberculous meningitis with subarachnoid block or impending block when used concurrently with appropriate antituberculous chemotherapy
Trichinosis with neurologic or myocardial involvement

CONTRAINDICATIONS

Systemic fungal infections and known hypersensitivity to components.

WARNINGS

In patients on corticosteroid therapy subjected to unusual stress, increased dosage of rapidly acting corticosteroids before, during, and after the stressful situation is indicated.

Corticosteroids may mask some signs of infection, and new infections may appear during their use. Infections with any pathogen including viral, bacterial, fungal, protozoan or helminthic infections, in any location of the body, may be associated with the use of corticosteroids alone or in combination with other immunosuppressive agents that affect cellular immunity, humoral immunity, or neutrophil function.¹

These infections may be mild, but can be severe and at times fatal. With increasing doses of corticosteroids, the rate of occurrence of infectious complications increases.² There may be decreased resistance and inability to localize infection when corticosteroids are used.

Prolonged use of corticosteroids may produce posterior subcapsular cataracts, glaucoma with possible damage to the optic nerves, and may enhance the establishment of secondary ocular infections due to fungi or viruses.

Usage in pregnancy

Since adequate human reproduction studies have not been done with corticosteroids, the use of these drugs in pregnancy, nursing mothers or women of child-bearing potential requires that the possible benefits of the drug be weighed against the potential hazards to the mother and embryo or fetus. Infants born of mothers who have received substantial doses of corticosteroids during pregnancy, should be carefully observed for signs of hypoadrenalism.

Average and large doses of hydrocortisone or cortisone can cause elevation of blood pressure, salt and water retention, and increased excretion of potassium. These effects are less likely to occur with the synthetic derivatives except when used in large doses. Dietary salt restriction and potassium supplementation may be necessary. All corticosteroids increase calcium excretion.

Administration of live or live, attenuated vaccines is contraindicated in patients receiving immunosuppressive doses of corticosteroids. Killed or inactivated vaccines may be administered to patients receiving immunosuppressive doses of corticosteroids; however, the response to such vaccines may be diminished. Indicated immunization procedures may be undertaken in patients receiving nonimmunosuppressive doses of corticosteroids.

The use of DELTASONE Tablets in active tuberculosis should be restricted to those cases of fulminating or disseminated tuberculosis in which the corticosteroid is used for the management of the disease in conjunction with an appropriate anti-tuberculous regimen. If corticosteroids are indicated in patients with latent tuberculosis or tuberculin reactivity, close observation is necessary as reactivation of the disease may occur. During prolonged corticosteroid therapy, these patients should receive chemoprophylaxis. Persons who are on drugs which suppress the immune system are more susceptible to infections than healthy individuals. Chicken pox and measles, for example, can have a more serious or even fatal course in non-immune children or adults on corticosteroids. In such children or adults who have not had these diseases, particular care should be taken to avoid exposure. How the dose, route and duration of corticosteroid administration affects the risk of developing a disseminated infection is not known. The contribution of the underlying disease and/or prior corticosteroid treatment to the risk is also not known. If exposed to chicken pox, prophylaxis with varicella zoster immune globulin (VZIG) may be indicated. If exposed to measles, prophylaxis with pooled intramuscular immunoglobulin (IG) may be indicated. (See the respective package inserts for complete VZIG and IG prescribing information.) If chicken pox develops, treatment with antiviral agents may be considered. Similarly, corticosteroids should be used with great care in patients with known or suspected Strongyloides (threadworm) infestation. In such patients, corticosteroid-induced immunosuppression may lead to Strongyloides hyperinfection and dissemination with widespread larval migration, often accompanied by severe enterocolitis and potentially fatal gram-negative septicemia.

PRECAUTIONS

General Precautions

Drug-induced secondary adrenocortical insufficiency may be minimized by gradual reduction of dosage. This type of relative insufficiency may persist for months after discontinuation of therapy; therefore, in any situation of stress occurring during that period, hormone therapy should be reinstated. Since mineralocorticoid secretion may be impaired, salt and/or a mineralocorticoid should be administered concurrently.

There is an enhanced effect of corticosteroids on patients with hypothyroidism and in those with cirrhosis.

Corticosteroids should be used cautiously in patients with ocular herpes simplex because of possible corneal perforation.

The lowest possible dose of corticosteroid should be used to control the condition under treatment, and when reduction in dosage is possible, the reduction should be gradual.

Psychic derangements may appear when corticosteroids are used, ranging from euphoria, insomnia, mood swings, personality changes, and severe depression, to frank psychotic manifestations. Also, existing emotional instability or psychotic tendencies may be aggravated by corticosteroids.

Steroids should be used with caution in nonspecific ulcerative colitis, if there is a probability of impending perforation, abscess or other pyogenic infection; diverticulitis; fresh intestinal anastomoses; active or latent peptic ulcer; renal insufficiency; hypertension; osteoporosis; and myasthenia gravis.

Growth and development of infants and children on prolonged corticosteroid therapy should be carefully observed.

Kaposi's sarcoma has been reported to occur in patients receiving corticosteroid therapy. Discontinuation of corticosteroids may result in clinical remission.

Although controlled clinical trials have shown corticosteroids to be effective in speeding the resolution of acute exacerbations of multiple sclerosis, they do not show that corticosteroids affect the ultimate outcome or natural history of the disease. The studies do show that relatively high doses of corticosteroids are necessary to demonstrate a significant effect. (See DOSAGE AND ADMINISTRATION.)

Since complications of treatment with glucocorticoids are dependent on the size of the dose and the duration of treatment, a risk/benefit decision must be made in each individual case as to dose and duration of treatment and as to whether daily or intermittent therapy should be used.

Convulsions have been reported with concurrent use of methylprednisolone and cyclosporin. Since concurrent use of these agents results in a mutual inhibition of metabolism, it is possible that adverse events associated with the individual use of either drug may be more apt to occur.

Drug Interactions

